9.4.4 SAFETY ANALYSES

Although this is not a dose-escalation trial, the following safety monitoring scheme will be employed in the initial enrollment phase of the trial:

The safety monitoring phase of the study will consist of up to 12 patients, whose adverse event profiles will be monitored continuously. If two or less number of patients in this initial cohort of 12 patients experience Grade 3+ adverse events attributable to the study regimen and not resolved through symptomatic treatments within 48 hours, the safety monitoring phase will be considered complete and the enrollment will continue. If three or more patients in this initial cohort of 12 patients experience Grade 3+ adverse events attributable to the study regimen and not resolved through symptomatic treatments within 48 hours, then the enrollment will be halted to discuss the safety measure of the protocol and possible amendments will be developed to address the safety concerns. As the adverse event profiles of the patients in this safety monitoring phase are followed closely, the safety monitoring

phase will be halted once the number of patients with Grade 3+ adverse events attributable to the study regimen and not resolved through symptomatic treatments within 48 hours go beyond two cases; therefore, the patient enrollment may be halted for safety evaluation before enrolling 12 patients. The above safety monitoring rules will be employed regardless of patient evaluability for the primary endpoints; however, to be included in the safety monitoring, it will be required that the patient received at least one dose of the study regimen and attribution of a given adverse event to the study regimen is clearly established as 'at least possibly attributable to the study regimen'.

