To mask the after taste/unpleasant taste of black seed oil in TQ Formula, enteric coating will be applied on the drug (and the placebo). Previous clinical studies using fish oil have shown enteric coating to be safe with the added benefit of improving compliance and enhancing gastric absorption by transient protection against gastric acidity [112].

Dosing Modifications

Based upon data from previous studies using blackseed oil capsules, the doses proposed in this protocol are within the maximum tolerated doses. However, dose reductions will be allowed per protocol as below (Table 4.3.1).

If a patient experiences a Grade 3 or greater drug-related AE after a dose of blackseed capsules upon evaluation per protocol, then the next dose will not be administered. The patient may receive additional doses of blackseed capsules, at the discretion of the PI, if the Grade 3 or greater event has resolved or has been reduced sufficiently as assessed by the treating PI prior to administration of the additional doses of blackseed capsules and dose reduction will be allowed as per Table 4.3.1 below.

Table 4.3.1: Dose modifications

Agent	Starting Dose (0 Dose Level)	-1 Dose Level	-2 Dose Level
Blackseed Oil Capsules/Placebo	500 mg, 3 capsules, orally twice a day (total 3g daily)	500 mg, 2 capsules, orally twice a day (total 2g daily)	500 mg, 1 capsule, orally twice a day (total 1g daily)

For Grade 3 or greater treatment related toxicity that cannot be controlled with symptomatic treatment within 48 hours, such as nausea and/or vomiting that can be controlled by antiemetics or diarrhea that can be controlled by anti-diarrheal medicines, the dose level will be decreased to dose level -1. Similarly, patients who develop Grade 3 treatment related toxicity that cannot be controlled with symptomatic treatment within 48 hours at dose level -1 will have further decrease in dosage to dose level -2. Finally, patients who develop Grade 3 treatment related toxicity that cannot be controlled with symptomatic treatment within 48 hours at dose level -2 will discontinue therapy. If the patient experiences significant toxicity requiring a dose reduction, the patient will remain at the lower dose level for subsequent cycles, i.e., dose re escalation is not allowed.

Patients should terminate study treatment if further reduction is indicated beyond the -2 level.

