8.3.6 SERIOUS ADVERSE EVENT REPORTING

Generally, any AE considered serious by the PI or Sub-investigator or which meets the definition of an SAE included in **Section 8.3.2, Definition of Serious Adverse Events** must be submitted on an SAE form to the Tranquil Clinical Research pharmacovigilance group (PVG).

The principal investigator or designee must immediately report to the sponsor any serious adverse event, whether or not considered drug related, including those listed in the protocol or investigator brochure and must include an assessment of whether there is a reasonable possibility that the drug caused the event [21 CFR 312.64(b)].

Upon identification, all SAEs will be reported by the site within 24 hours using the Initial SAE Report Form. The Initial SAE Report Form should be submitted Tranquil Clinical Research (CRO) within 24 hours either by e-mail (preferable) or by phone using the following contact information:

Email : [contact] [contact]

All serious adverse events (SAEs) will be followed until satisfactory resolution or until the site investigator deems the event to be chronic or the participant is stable. Other supporting documentation of the event may be requested by the study sponsor and should be provided as soon as possible.

The study sponsor will be responsible for notifying the Food and Drug Administration (FDA) of any unexpected fatal or life-threatening suspected adverse reaction as soon as possible, but in no case later than 7 calendar days after the sponsor's initial receipt of the information.

In addition, the sponsor must notify FDA and all participating investigators in an Investigational New Drug (IND) safety report of potential serious risks, from clinical trials or any other source, as soon as possible, but in no case later than 15 calendar days after the sponsor becomes aware and determines that the information qualifies for reporting.

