8.4.2 UNANTICIPATED PROBLEM REPORTING

The investigator will report unanticipated problems (UPs) to the reviewing Institutional Review Board (IRB) and to the Sponsor/CRO. The UP report will include the following information:

- Protocol identifying information: protocol title and number, PI's name, and the IRB project number;
- A detailed description of the event, incident, experience, or outcome;
- An explanation of the basis for determining that the event, incident, experience, or outcome represents an UP;
- A description of any changes to the protocol or other corrective actions that have been taken or are proposed in response to the UP.

To satisfy the requirement for prompt reporting, UPs will be reported using the following timeline:

- UPs that are serious adverse events (SAEs) will be reported according to the timelines noted in section 8.3.6.
- Any other UP will be reported to the IRB (per IRB policy) and to the CRO/study sponsor within a reasonable time period of the investigator becoming aware of the problem.

- All UPs should be reported to appropriate institutional officials (as required by an institution's written reporting procedures), the supporting agency head (or designee), and the Office for Human Research Protections (OHRP) as applicable, within the appropriate timeline (per institution policy) of the IRB's receipt of the report of the problem from the investigator.

[figure not shown]

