10.1.2 STUDY DISCONTINUATION AND CLOSURE

This study may be temporarily suspended or prematurely terminated if there is sufficient reasonable cause. Written notification, documenting the reason for study suspension or termination, will be provided by the suspending or terminating party to study participants, investigator, the Investigational New Drug (IND) sponsor and regulatory authorities.

If the study is prematurely terminated or suspended, the Principal Investigator (PI) will promptly inform study participants, the Institutional Review Board (IRB), and sponsor and will provide the reason(s) for

the termination or suspension. Study participants will be contacted, as applicable, and be informed of changes to study visit schedule.

Circumstances that may warrant termination or suspension include, but are not limited to:

- Determination of unexpected, significant, or unacceptable risk to participants i.e.- If three or more patients in the initial cohort of 12 patients experience Grade 3+ adverse events attributable to the study regimen and not resolved through symptomatic treatments within 48 hours, then the enrollment will be halted to discuss the safety measure of the protocol and possible amendments will be developed to address the safety concerns.
- Demonstration of efficacy that would warrant stopping
- Insufficient compliance to protocol requirements
- Data that are not sufficiently complete and/or evaluable
- Determination that the primary endpoint has been met
- Determination of futility

Study may resume once concerns about safety, protocol compliance, and data quality are addressed, and satisfy the sponsor, IRB and/or Food and Drug Administration (FDA).

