## 7.6 Interim Analysis and Data Monitoring

There is no planned interim analysis for the primary objective of the study; however, there will be safety interim analyses after the initial cohort of 12 patients have been enrolled and have received at least one dose of the assigned drug. This safety interim analysis will be conducted without unblinding the patients. As part of this safety interim analysis, if two or less number of patients in this initial cohort of 12 patients experience Grade 3+ adverse events attributable to the study regimen and not resolved through symptomatic treatments within 48 hours, there will be no need for unblinding the safety cohort; however, if there are 3 or more cases with Grade 3+ adverse events attributable to the study regimen and not resolved through symptomatic treatments within 48 hours, the enrollment will be halted, this initial cohort of patients will be unblinded to evaluate the distribution of the AEs between the placebo and the study drug, and the possible corrective amendments will be considered.

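### The 3-of-12 enrolment halt applies its 48-hour symptomatic-treatment qualifier to Grade 4 as well as Grade 3, so on its literal text a related, non-fatal Grade 4 reaction resolved within two days does not count

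*Protocol*

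**What the plan says.** Protocol 9.4.4 sets up a safety phase of up to 12 patients with continuous review of adverse events. Patients enter the count once they have taken at least one dose, and an event needs only possible attribution. The halting sentence covers Grade 3 or higher events "attributable to the study regimen and not resolved through symptomatic treatments within 48 hours, then the enrollment will be halted". The same qualifier appears in the sentence that declares the phase complete at two or fewer cases, and in the sentence that allows an early stop.

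Protocol 10.1.2 restates the rule ("If three or more patients in the initial cohort of 12 patients experience Grade 3+ adverse events attributable to the study regimen") under a list introduced by "Circumstances that may warrant termination or suspension include, but are not limited to".

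SAP 7.6 uses the same count to decide whether the cohort is unblinded. At two or fewer cases, "there will be no need for unblinding the safety cohort". The other branch applies "if there are 3 or more cases with Grade 3+ adverse events attributable to the study regimen and not resolved" under the same 48-hour condition. Enrolment then stops and the events are compared by arm.

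Neither document defines symptomatic treatment or resolution. The nearest guidance is in the dose-reduction rule of Protocol 4.3, which gives examples: "such as nausea and/or vomiting that can be controlled by antiemetics or diarrhea that can be controlled by anti-diarrheal medicines".

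**The concern.** A 48-hour allowance makes sense for a Grade 3 event such as vomiting that an antiemetic settles. It makes less sense for a life-threatening reaction, whose importance does not depend on how quickly it was reversed. The rule puts Grade 3 and above in one category and applies the allowance to all of it.

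This count is the only provision that makes an enrolment halt mandatory, and in SAP 7.6 it alone triggers the comparison by arm. Protocol 10.1.6 says there is no data and safety monitoring board. Two people applying the same sentence could count the same short, related Grade 4 reaction differently. On the literal reading, three such reactions leave the count at zero, the phase is declared complete and the cohort stays blinded.

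**Working it through.** **Text check.** The qualifier occurs six times: three in Protocol 9.4.4, one in 10.1.2 and two in SAP 7.6. Each time, attribution and non-resolution are joined by *and*, so an event that fails either condition is not counted. No occurrence exempts Grade 4. Even if all 12 patients had related Grade 4 reactions that symptomatic treatment resolved within 48 hours, the literal count would be 0. A death cannot resolve, so Grade 5 counts on any reading.

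**Inputs.** From the documents: threshold 3, cohort 12, 1:1 allocation in blocks of 4 within site (Protocol 9.2), hence about 6 of the 12 on active drug. The documents state no operating characteristics for the rule, so there is no figure to reproduce, and they give no Grade 4 rates. The rates below (1% to 10%), the share of events resolved within 48 hours and the site split are assumptions.

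**Formula.** P(X ≥ 3) = 1 − P(0) − P(1) − P(2), with X binomial(n, rate).

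**Gain: drug-caused Grade 4 events, n = 6 on active, all counted.** At 10%: 1 − 0.5314 − 0.3543 − 0.0984 = 0.0159.

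| Rate | All counted | Now, if half resolve within 48 h | Now, if all resolve within 48 h |
|---|---|---|---|
| 1% | 0.002% | under 0.001% | 0 |
| 5% | 0.22% | 0.03% | 0 |
| 10% | 1.6% | 0.2% | 0 |

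The number on active drug may differ from 6. With 5 or 7, the 10% figure is 0.9% or 2.6%. If two sites enrol 6 patients each, the last two at each site come from a part-filled block. The number on active is then 4, 5, 6, 7 or 8 with probabilities 1/36, 8/36, 18/36, 8/36 and 1/36. Thus 5 to 7 covers 34/36 = 94% of allocations, and the average halt probability at 10% is 1.7%.

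**Cost: background Grade 4 events judged at least possibly related, n = 12, both arms blinded.** At 10%: 1 − 0.2824 − 0.3766 − 0.2301 = 0.1109. Grade 4 events lasting over 48 hours already count, so the added risk is the total minus what the present rule gives. The last two columns assume that half already count, so the present rate is half the stated rate.

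| Rate | Total | Present rule | Added |
|---|---|---|---|
| 1% | 0.02% | 0.003% | 0.02 points |
| 2% | 0.15% | 0.02% | 0.13 points |
| 5% | 2.0% | 0.3% | 1.7 points |
| 10% | 11.1% | 2.0% | 9.1 points |

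On the same half-resolved basis, the gain is 0.22 − 0.03 = 0.19 points at 5% and 1.59 − 0.22 = 1.4 points at 10%. The totals are upper bounds on the added risk from Grade 4 events taken alone. Both tables leave out unresolved Grade 3 events, which share the count of three; including them could raise either figure.

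**The case against.** The strongest objection is that the wording already excludes these events from the allowance. The only examples in the documents are antiemetics and anti-diarrheals, and emergency treatment of a life-threatening reaction fits that company poorly. This narrow reading is reasonable, but it does not settle the matter. Protocol 4.3 applies the same 48-hour idea to Grade 3 or greater toxicity, also without a Grade 4 exception, and the halting rule does not refer to 4.3.

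A reader might infer that such reactions could pass unnoticed or that nobody could act on them. The documents do not support that:

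- Serious events reach the CRO within 24 hours, and FDA must be told of any "unexpected fatal or life-threatening suspected adverse reaction as soon as possible, but in no case later than 7 calendar days"; other serious risks go to FDA and investigators within 15 days (Protocol 8.3.6).
- Unanticipated-problem reports to the IRB include "A description of any changes to the protocol or other corrective actions that have been taken or are proposed" (8.4.2).
- The patient's next dose is withheld (4.3), and an individual can be unblinded in an emergency (6.3).
- Blinded adverse-event monitoring reports run during the study (SAP 5.3.6).
- The study may be suspended for unacceptable risk (10.1.2).

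These safeguards stand, and they confine the gap to automatic triggering. They require reporting, protect the individual or permit a pause. None obliges an enrolment halt or the comparison by arm.

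It is also fair to say that, at equal assumed rates, the added chance of a background pause exceeds the gain in drug-caused halts. The case for the change therefore rests on what the rule ought to count, with little support from detection probability.

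**Conclusion.** The point holds as a gap in the rule for its most serious non-fatal events. On the literal text, a related Grade 4 reaction resolved with symptomatic treatment within 48 hours does not count toward the only mandatory halt, although a narrower reading is open. The gain in halt probability is small: 0.2% at an assumed 5% rate and 1.6% at 10%, with six on active and all such events now excluded. A reader might infer that closing the gap would make the run-in sensitive to rare reactions. It would not; at a 1% rate the figure is 0.002%. The sizes depend on the assumed rates and shares. The textual finding does not. This is a cheap change that the sponsor could make, with low priority.

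**What to change.** Define a counted event once in Protocol 9.4.4 and use the definition in all six places. A patient counts if either of these occurs and is at least possibly attributable to the study regimen:

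- any Grade 4 or 5 adverse event, whatever its time to resolution. For events outside CTCAE, use life-threatening or fatal, because the fallback scale in Protocol 8.3.3.1 stops at severe;
- a Grade 3 event that symptomatic treatment has not resolved within 48 hours, where symptomatic treatment means supportive care of the kind listed in Protocol 4.3, such as antiemetics and anti-diarrheals.

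The second part matters, since moving Grade 4 alone would leave the term undefined for Grade 3. Do not add related serious events of any grade: COVID-19 hospitalizations in both blinded arms could then trigger the halt. The threshold of 3, the cohort of 12, the blinded review and the dose-reduction rule stay as they are.

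The cost is an edit to two documents. Grade and attribution are already recorded, so no new data or committee is needed. The downside is an occasional pause from background events, at most 0.02%, 0.15%, 2.0% and 11.1% at assumed rates of 1%, 2%, 5% and 10% (Grade 4 events alone), because Protocol 8.3.3.2 sets a low bar for attribution. Protocol 8.3.5 limits this: a laboratory abnormality is an adverse event only when it is clinically significant and produces signs or symptoms, so isolated Grade 4 laboratory values would not count.

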9.4.5 BASELINE DESCRIPTIVE STATISTICS

9.4.6 PLANNED INTERIM ANALYSES

This section is not applicable for the analysis of the primary and secondary objectives; however, there will be safety interim analyses after the initial cohort of 12 patients have been enrolled and have received at least one dose of the assigned drug.

9.4.7 SUB-GROUP ANALYSES

In analyses for primary and secondary endpoints, age, gender, race and other demographics and clinical factors and markers may be used as control variables as appropriate; however, the statistical design of this study does not include any planned subgroup analyses. All subgroup analyses if found appropriate will be considered exploratory to generate hypotheses for future prospective studies.

9.4.8 TABULATION OF INDIVIDUAL PARTICIPANT DATA

Patient specific data will be presented by study arm, including patient demographics and baseline clinical factors and measures.

9.4.9 EXPLORATORY ANALYSES

The study includes exploratory objectives for the PK profile of the study drug and measurement of the immune response through cytokine production, coagulation factors and various effector immune cell subsets in the PBMC of these patients on Day 1, Day 7 and 14 using FACS. The details of the analytic approaches for these exploratory objectives will be shared in the study SAP. Analyses to address these two exploratory aims will be detailed in the study SAP.

10 SUPPORTING DOCUMENTATION AND OPERATIONAL CONSIDERATIONS

10.1 REGULATORY, ETHICAL, AND STUDY OVERSIGHT CONSIDERATIONS

10.1.1 INFORMED CONSENT PROCESS

10.1.1.1 CONSENT/ASSENT AND OTHER INFORMATIONAL DOCUMENTS PROVIDED TO PARTICIPANTS

In obtaining and documenting informed consent, the investigator must comply with applicable regulatory requirements (e.g., 45 CFR Part 46, 21 CFR Part 50, 21 CFR Part 56) and should adhere to ICH GCP.

Prior to the beginning of the trial, the investigator should have the IRB's written approval for the protocol and the written informed consent form(s) and any other written information to be provided to the participants.

Consent forms describing in detail the study intervention, study procedures, and risks are given to the participant and written documentation of informed consent is required prior to starting intervention/administering study intervention.

10.1.1.2 CONSENT PROCEDURES AND DOCUMENTATION

Informed consent is a process that is initiated prior to the individual's agreeing to participate in the study and continues throughout the individual's study participation. Consent forms will be Institutional Review Board (IRB)-approved and the participant will be asked to read and review the document. The investigator will explain the research study to the participant and answer any questions that may arise. A verbal explanation will be provided in terms suited to the participant's comprehension of the purposes, procedures, and potential risks of the study and of their rights as research participants. Participants will have the opportunity to carefully review the written consent form and ask questions prior to signing. The participants should have the opportunity to discuss the study with their family or surrogates or think about it prior to agreeing to participate. The participant will sign the informed consent document prior to any procedures being done specifically for the study. Participants must be informed that participation is voluntary and that they may withdraw from the study at any time, without prejudice. A copy of the informed consent document will be given to the participants for their records. The informed consent process will be conducted and documented in the source document (including the date), and the form signed, before the participant undergoes any study-specific procedures. The rights and welfare of the participants will be protected by emphasizing to them that the quality of their medical care will not be adversely affected if they decline to participate in this study.

10.1.2 STUDY DISCONTINUATION AND CLOSURE

This study may be temporarily suspended or prematurely terminated if there is sufficient reasonable cause. Written notification, documenting the reason for study suspension or termination, will be provided by the suspending or terminating party to study participants, investigator, the Investigational New Drug (IND) sponsor and regulatory authorities.

If the study is prematurely terminated or suspended, the Principal Investigator (PI) will promptly inform study participants, the Institutional Review Board (IRB), and sponsor and will provide the reason(s) for

the termination or suspension. Study participants will be contacted, as applicable, and be informed of changes to study visit schedule.

Circumstances that may warrant termination or suspension include, but are not limited to:

- Determination of unexpected, significant, or unacceptable risk to participants i.e.- If three or more patients in the initial cohort of 12 patients experience Grade 3+ adverse events attributable to the study regimen and not resolved through symptomatic treatments within 48 hours, then the enrollment will be halted to discuss the safety measure of the protocol and possible amendments will be developed to address the safety concerns.
- Demonstration of efficacy that would warrant stopping
- Insufficient compliance to protocol requirements
- Data that are not sufficiently complete and/or evaluable
- Determination that the primary endpoint has been met
- Determination of futility

Study may resume once concerns about safety, protocol compliance, and data quality are addressed, and satisfy the sponsor, IRB and/or Food and Drug Administration (FDA).

